6 = College degree

7 = Some graduate work

8 = Master's degree

9 = Doctoral degree

10 = Other _____

98 = Refuse to Answer

What best describes your current employment status?

1 = Working full-time

2 = Working part-time

3 = Working equivalent of full-time job through part-time jobs

4 = Unemployed and looking for work

5 = Unemployed and not looking for work

6 = School full-time

7 = School part-time

8 = Both work and school

9 = Other _____

98 = Refuse to Answer

Thinking about the last 12 months, on average, after taxes, how much was your total net (take home) income per MONTH? Include all your sources of income (workers comp, student loan, Social Security, etc.).

- 1 = Less than \$500**
- 2 = Between \$501 & \$1000**
- 3 = Between \$1001 & \$1500**
- 4 = Between \$1501 & \$2000**
- 5 = Between \$2001 & \$2500**
- 6 = Between \$2501 & \$3000**
- 7 = Between \$3001 & \$3500**
- 8 = Between \$3501 & \$4000**
- 9 = Between \$4001 & \$6000**
- 10 = Between \$6001 & \$8000**
- 11 = More than \$8000**
- 98 = Refuse to Answer**

What is the zip/postal code where you currently live? _____

Screener

Safety and preliminary efficacy of combination photodynamic therapy with 5-aminolevulinic acid and microcurrent therapy for the treatment of acne vulgaris

Date: _____ Screener: _____

Recruitment Source: _____

1. How old are you?

_____ (if less than 18 INELIGIBLE and HALT screener,
if older than 30, INELIGIBLE but continue screener)

2. Are you pregnant or do you suspect being pregnant?

Yes No (if yes, INELIGIBLE but continue screener)

3. Are you actively trying to get pregnant?

Yes No (if yes, INELIGIBLE but continue screener)

4. Are you planning to get pregnant in the next 3 months?

Yes No (if yes, INELIGIBLE but continue screener)

5. Are you taking oral contraceptive pills?

Yes No (if yes, INELIGIBLE but continue screener)

6. Are you breastfeeding/lactating?

Yes No (if yes, INELIGIBLE but continue screener)

7. Are you taking any medication for your acne?

Yes No

If yes what kind of medication? * _____

When was the last time you took your medication? _____

If oral retinoids in the past 6 months (INELIGIBLE but continue screener)

If oral antibiotic within the last 30 days (INELIGIBLE but continue screener)

If have received topical acne treatment (i.e. retinoids, antibiotics and anti-inflammatory agents or chemical peeling) within the last 30 days (INELIGIBLE but continue screener)

* If respondent does not remember their medication ask the following probes:

- can you describe the medication... is it a pill? Is it a cream or lotion that you put on your skin?
How often do you use it? If the respondent still cannot remember explain that this information is important and ask them to provide it by contacting the research team, asking their provider, or other reasonable steps.

(Continue screening but do not enroll because eligibility cannot be determined)

8. Do you have history of photo-sensitive dermatitis?

Yes No (if yes, INELIGIBLE but continue screener)

9. Do you have a pacemaker?

Yes No (if yes, INELIGIBLE but continue screener)

Eligible and enrolled

_____ Eligible not interested

_____ Ineligible

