entry, analysis and associated activities may be conducted at offices of the Behavioral Health Promotion Program located at [name].

G. Dates of Study

We plan to initiate the study as soon as we obtain approval from the IRB. We anticipate completing all study activities by March 2016.

H. Subjects/Participants

H1. Sample Size, Composition and Eligibility Requirements

We are planning to recruit up to 60 males and females with mild to moderate facial acne to participate in this study. (Mild to moderate acne is operationally defined as being acne severity grade 2-4 on the Leeds grading system) To be eligible, participants must: 1) be ages 18 to 30; 2) have mild to moderate facial acne; 3) have skin type II-V as measured in the Fitzpatrick Scale; 4) be able to understand written and/or spoken English; and 5) be able to provide written informed consent.

Individuals who: 1) have been treated with oral retinoids in the past 6 months; and/or 2) have been treated with oral antibiotic within the last 30 days; and/or 3) have received topical acne treatment (i.e. retinoids, antibiotics and anti-inflammatory agents or chemical peeling) within the last 30 days; 4) are pregnant or lactating; 5) have history of photo-sensitive dermatitis; 6) are taking oral contraceptive pills (OCP); and 7) have pacemaker will not be eligible to participate.

H2. Subject Selection and Recruitment.

We will use both active and passive recruitment approaches. Active recruitment will primarily consist of direct referrals from physicians at NSU Ziff Clinic Division of Dermatology, General, Cosmetic Dermatology and Cutaneous Surgery or other dermatology providers in South Florida. To complement our active recruitment strategies we will also engage in passive recruitment which will include: 1) e-mail announcements distributed via list-serves; and 2) distributing and/or posting project flyers at bulletin boards, community organizations etc.

H2.1 Active recruitment approaches

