Research staff will briefly describe the study and requirements for participation. Interested individuals will be invited to complete the eligibility screener. If permission is granted, staff will administer the eligibility screen and invite all eligible individuals to enroll in the study. We will obtain written informed consent from all eligible individuals wishing to participate in the study. After obtaining informed consent, we will complete the locator/enrollment form, select the randomization envelope (See section 1), and inform participants of their condition assignment. Research staff will ascertain whether the participant has sufficient time available at the current visit to complete the baseline assessment and receive the initial treatment. This is important because the time required to complete the treatment varies by condition (See Table 1). Participant who have sufficient time will complete the baseline assessment and will be given first treatment immediately following the informed consent process. Those who do not, will be scheduled to complete these activities at a subsequent visit. Individuals who do not wish to proceed through any point described above and those who screen not eligible, will be thanked for their interest and encouraged to seek treatment at the Ziff Clinic or any other dermatology provider.

Although we anticipate that the majority of screeners will be completed face-to-face, it is possible that some individuals may contact research staff via telephone. In this case, staff will describe the study and obtain permission to conduct a preliminary eligibility screen over the telephone using the above referenced procedures. If the potential participant is eligible, we will make an in-person appointment where we will confirm eligibility by re-administering the screening questionnaire, obtain informed consent, complete locator/enrollment form, assign to treatment conditions, and administer the baseline assessment along with the first treatment. As part of the scheduling process, we will explain that the duration of the study visit will be contingent upon their condition assignment and the maximum time that may be required for the initial visit will be approximately 4 hours. Consequently, we will schedule their initial appointments at a time during which they have 4 hours available for the visit.

H3. Informed Consent Procedures.

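### Screener item 7 opens with current acne medication while H1 excludes by look-back, so people who recently stopped treatment, or had a peel, may be enrolled despite H1

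*Combined protocol and SAP*

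**What the plan says.** Section H1 (Sample Size, Composition and Eligibility Requirements) lists three treatment exclusions, all by look-back. The first covers people who "have been treated with oral retinoids in the past 6 months". The second is an oral antibiotic within 30 days. The third is topical acne treatment within 30 days, with chemical peeling among the examples. None requires that the treatment be current.

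The Screener, under Data Collection Forms and Measures, has one item on treatment, item 7. It reads, in order:

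- the opening yes/no question, "Are you taking any medication for your acne";
- "If yes what kind of medication";
- "When was the last time you took your medication";
- three classification lines: "If oral retinoids in the past 6 months (INELIGIBLE but continue screener", "If oral antibiotic within the last 30 days (INELIGIBLE but continue screener", and "If have received topical acne treatment (i.e. retinoids, antibiotics and anti-inflammatory agents or chemical peeling) within the last 30 days", the last also leading to ineligible;
- memory probes for a respondent who cannot name the medication.

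Section H2.3 says that staff administer the screener. For people first screened by telephone, it says of the in-person visit that "we will confirm eligibility by re-administering the screening questionnaire". Section 3.I answers no to obtaining data from the medical record.

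**The concern.** A form that carries out a look-back exclusion should ask about the past. Item 7 asks first about the present, and about medication for acne. Three kinds of people can truthfully say no while inside an H1 window: someone who stopped an oral retinoid two months ago, someone who finished an oral antibiotic course for another condition, and someone who had a chemical peel two weeks ago, since a peel is not a medication that one takes.

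Such people are plausible here. Section H2.1 recruits mainly through a dermatology clinic, including its existing acne patients, and through other dermatologists. If enrolled, they bring residual effect of, or relapse after, the earlier treatment into lesion count, sebum and severity. With up to 60 participants in three arms, about 20 per arm, a few such people can add visible noise and may fall unevenly by chance. Each would also be an eligibility deviation.

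**Working it through.** **Side-by-side reading.** The documents contain no calculation on this point, so the main check is textual.

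| H1 exclusion | Rule printed in item 7? | Question that reaches a respondent who answers no? |
|---|---|---|
| Oral retinoid, 6 months | Yes, same window | None stated |
| Oral antibiotic, 30 days | Yes, same window | None stated; the opening question is also limited to acne |
| Topical acne treatment or peel, 30 days | Yes, same window | None stated; no question names peels |

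The windows agree between H1 and the form. The gap lies in the route to them. The line on type of medication is expressly tied to a yes. The last-use line speaks of the respondent's medication, which presupposes one. The three windows are rules for classifying an answer, not questions put to the respondent. Items 1 to 6, 8 and 9 cover age, pregnancy, oral contraceptives, lactation, photosensitive dermatitis and pacemaker, and none asks about past acne treatment.

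**Is there a second check?** Repeating the form after a telephone screen repeats the gap. Section 3.I rules out data from the medical record. No other check appears in the readable text.

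**Possible numbers.** Let q be the share of the 60 entrants who are inside a window. The documents do not give q, so these values are assumptions. Expected number = 60q; chance of at least one = 1 − (1 − q)^60.

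| q | Expected of 60 | Expected per arm of 20 | Chance of at least one |
|---|---|---|---|
| 1% | 0.6 | 0.2 | 45% |
| 2% | 1.2 | 0.4 | 70% |
| 5% | 3 | 1 | 95% |
| 10% | 6 | 2 | 99.8% |
| 20% | 12 | 4 | about 100% |

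**Illustration of dilution.** The plan states no alpha, power or effect size. Suppose a two-sample t-test, 20 per arm, two-sided 0.05; 80% power then needs a difference of 0.909 SD. If a share q loses a fraction k of the effect and the SD is unchanged, the difference becomes 0.909 × (1 − kq).

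| q | Power, all effect lost (k = 1) | Power, half lost (k = 0.5) |
|---|---|---|
| 1% | 79.2% | 79.6% |
| 2% | 78.4% | 79.2% |
| 5% | 75.9% | 78.0% |
| 10% | 71.3% | 75.9% |
| 20% | 61.1% | 71.3% |

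**The case against.** The form is not blind to past use. It prints a last-use question and all three windows, peels included, in front of a trained interviewer, and only the type-of-medication line is expressly conditional on a yes. A careful interviewer could apply the windows to everyone. This stands, and it rules out saying that the form asks only about current use. It does not close the gap, because nothing instructs staff to do so.

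The screener cannot be the whole eligibility decision either: it has no item on Leeds grade or Fitzpatrick type, both required by H1, so staff must apply H1 beyond the form. Staff also describe the requirements for participation before screening, and recent treatment may surface then. A reader might infer that ineligible people will be enrolled. The documents support only that they may be, since the H1 exclusions still bind.

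A reader might also infer that no second check exists. That cannot be settled. Section 3.E, on inclusion and exclusion, is cut off in the available text and some pages are missing. Re-administration is described only for telephone screens, whereas most screening is expected face to face. The answer in 3.I concerns obtaining data, not confirming eligibility.

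Finally, the power table could be taken as evidence of impact. It is not. The shares, the loss of effect and the 80% starting point are all assumptions, and the plan names repeated measures analysis of variance rather than this t-test.

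**Conclusion.** The concern holds as a mismatch between form and protocol. Administered literally, item 7 can pass people whom H1 excludes, and the peel exclusion has no question behind it at all. How many would pass cannot be worked out from the documents. Even at an assumed 1% to 2%, the chance of at least one among 60 is 45% to 70%. At those shares the illustrative power loss is below 2 points; it becomes material only at shares of roughly 5% to 10% or more, and then chiefly if affected people lose the whole effect.

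It would be tempting to call this a source of bias between arms. The documents do not support that: the same screener is used before assignment for everyone, and assignment is randomised in blocks of 6. The expected consequence is added noise, possible dilution and chance imbalance. The case for changing the form rests on H1 being applied as written, not on the power figures.

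One part depends on interpretation. H1 limits the topical exclusion to acne treatment but puts no such limit on oral antibiotics. Read literally, an antibiotic for any indication excludes, and item 7's restriction to acne medication then misses it. The sponsor should confirm that reading.

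**What to change.** Reconcile item 7 with H1 by replacing the opening question with three stand-alone questions asked of every respondent, using H1's existing wording and windows:

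1. Oral retinoid in the past 6 months (yes/no).
2. Oral antibiotic in the last 30 days (yes/no), with the indication worded as the sponsor confirms for H1.
3. Topical acne treatment or chemical peel in the last 30 days (yes/no).

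Each yes leads to ineligible. Keep the memory probes for anyone unsure, with the existing rule not to enrol while eligibility is undetermined. A lesser alternative is an instruction that the look-back lines are asked of everyone whatever the first answer, with peels named in a question.

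The cost is rewording one item on a short form. A few more people will screen out, all of them already excluded by H1; for antibiotics taken for another condition, that depends on the sponsor confirming the literal reading. No eligibility window changes.
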